#### BACKGROUND

Hypertension is the most important risk factor for the morbidity and mortality of cardiovascular and cerebrovascular diseases in China. Useful treatment of hypertension can reduce the incidence of cardiovascular and cerebrovascular diseases. Hemodynamic overload caused by hypertension can lead to left ventricular remodeling and functional changes, usually manifested as significant changes in the geometric configuration of the left ventricle, such as concentric hypertrophy (CH) and eccentric hypertrophy (EH). Left ventricular hypertrophy is an adaptive process after the increase of hemodynamic load, and also cause damages of target organs. Studies have shown that left ventricular hypertrophy (LVH) and left atrial enlargement caused by hypertension are independent risk factors for cardiovascular events. Epidemiological studies have confirmed that changes in the geometry of left ventricular remodeling may be harmful and increase the risk of incidence rate and mortality of cardiovascular disease. The different types of left ventricular remodeling are related to cardiovascular events and all-cause mortality. Different left ventricular geometric configurations had different prognosis. Studies show that CH has the larger left ventricular mass and worse prognosis, than EH, concentric remodeling (CR) and normal left ventricular geometry (NG). In patients with essential hypertension, ventricular remodeling and hypertrophy always occur, and myocardial diastolic and systolic function decline gradually, eventually leading to heart failure. Another study showed that the mortality of patients transferred from CR to NG significantly decreased, and the mortality of patients transferred from CR to LVH was significantly higher. Antihypertensive treatment could significantly reduce LVH and prevent or reverse the abnormal geometry of left ventricle. Therefore the type, distribution characteristics and configuration outcome of left ventricular hypertrophy remodeling, evaluate left ventricular systolic and diastolic function and left atrial size can improve the early prevention and attention of heart failure, and early intervention and treatment are of great significance for reducing the occurrence of cardiovascular events and evaluating the progress and prognosis of the

disease.

Most researches on hypertension configuration adopt the Ganau classification, and evaluation of left ventricular hypertrophy ultrasonic technology in hypertension guidelines is also based on this classification standard. However, the reference values in this classification standard, including left ventricular mass index (LVMI) and relative wall thickness (RWT), are from European and American populations. It is not clear whether the criteria for defining the type of left ventricular remodeling is suitable for the Chinese population, and whether this classification method has an impact on the constituent ratio of left ventricular remodeling types. As we all know, the normal value of left ventricular mass (LVM) varies with gender, race, age, height and weight. Now body surface area (BSA) is usually used for index, but always over corrected. The international reference standard for left ventricular configuration recommended in the 2015 ASE/EACVI guidelines for quantitative measurement of adult heart echocardiography, in which the left ventricular mass is indexed by BSA, and its abnormal threshold is LVMI>115g/m2 (male) or LVMI>95g/m^2 (female). The newly issued hypertension management guidelines in 2018 mentioned that height2.7 should be used to calibrate LVM to define left ventricular hypertrophy, and its abnormal threshold is>50 g/m2.7 (male) or>47 g/m2.7 (female). The two different index methods affecting the configuration distribution characteristics remains to be determined. Recent studies have found that the normal reference values of the echocardiographic parameters from Chinese and Western people are different. With the normal reference values of echocardiographic parameters in the Study of Echocardiographic Measurements for Normal Chinese Han Adults (EMINCA Study), LVM was indexed by the two above indexed methods, to speculate that the range of normal reference values of LVMI and RWT, the indicators for Ganau classification, were different from those recommended in previous European and American guidelines, and the distribution of hypertension configurations was also different, as well as in WASE study.

Persistent hemodynamic overload in patients with hypertension will not only lead to myocardial remodeling and ventricular and atrial remodeling, but also seriously damage the function of ventricle and atrium. The early cardiac damage in patients with hypertension is mainly manifested as left ventricular hypertrophy, left atrial enlargement and other remodeling phenomena. With long-term high blood pressure, myocardial fibers will increase thickness, which will lead to reduction of myocardial compliance, increase of left ventricular filling pressure, and damage the diastolic function of the heart. When the left ventricular hypertrophy caused by long-term high blood pressure exceeds the compensatory threshold of the heart, it will inhibit the pumping function of the heart and reduce the contractility of the myocardium. When the disease continues to progress, it will even cause the continuous expansion of the heart cavity, increase of the tension of the ventricular wall and cause heart failure with reduced systolic function. Except for LVEF, the global longitudinal strain (GLS) of the left ventricle is more sensitive to the early damage of the left ventricular myocardium and has predictive value, which is widely concerned by people. LVGLS is affected by the wall shear stress, myocardial ischemia and myocardial fibrosis. Recently some studies have found that the increase of left ventricular afterload is significantly related to the decrease of GLS. Myocardial work (MW), a new indicator of the combination of GLS and cardiac afterload, can reflect the changes of the heart at the early stage of many diseases including assessing the systolic capacity of the heart and reflecting the remodeling of the left ventricle. With the construction and analysis of left ventricular pressure volume loop (PSL), we can get the global work index (GWI), global constructive work (GCW), global wasted work (GWW) and global work efficiency (GWE) of myocardium. Therefore, the index of myocardial work can provide us with more information about ventricular remodeling and afterload changes, which is helpful for us to evaluate the left ventricular remodeling caused by afterload changes.

Echocardiography is a commonly used clinical examination method, with ease of operation, safety, non-invasive, real-time imaging, strong repeatability, low cost and so on, which is widely used to evaluate the structure and function of the heart and cardiac hemodynamics. Framingham et al. found that there is a strong correlation between LVM detected by echocardiography and the incidence rate and mortality of cardiovascular diseases, and LVM is also the most commonly used tool for clinical diagnosis of left ventricular diastolic dysfunction (LVDD).

The LVM and LAV derived from the normal value data of Chinese healthy adults have been reported to be different from the recommended reference values in guidelines, and the distribution characteristics of hypertension remodeling are also different. However, this difference still lacks of large multi-center research to further confirm it. Meanwhile, the characteristics and outcomes of cardiac remodeling in Chinese hypertensive population and whether this difference in configuration has an impact on the treatment, prognosis and cardiovascular events of hypertensive population are still needed to be explored.

#### **OBJECTIVES:**

This study was to observe the relationship between blood pressure and cardiovascular remodeling evaluated by different standards in hypertensive population; to compare the relationship between different cardiac configurations and cardiovascular events in Chinese hypertensive population.

#### **RESEARCH DESIGN**

Studies have shown that different configurations of left ventricle and left atrial enlargement in hypertensive patients can predict the occurrence of cardiovascular events. The standards of left ventricular remodeling and left atrial enlargement based on European and American populations may not be applicable to Chinese populations. This study was a multicenter study to verify different left ventricular remodeling in Chinese hypertensive population, and explore the influence of different left ventricular remodeling standards on the treatment options and prognosis.

#### **Participant:**

Participants with essential hypertension and healthy volunteers in the outpatient and hospital in research centers.

#### Groups:

Healthy volunteers: volunteers without chronic disease history such as hypertension, diabetes, coronary heart disease, cerebrovascular disease, and transthoracic echocardiography showed normal cardiac structure and function.

Hypertensions: grouped with ultrasonic cardiogram parameters (including LVMI, RWT and LAVI)

## (1) Left ventricle remodeling groups: 2015 ASE/EACVI guideline standard:

Normal left ventricular geometry, NG: LVMI≤115g/m^2 (male) or LVMI≤95g/m^2 (female) and RWT≤0.42

Concentric remodeling, CR: LVMI $\leq 115$ g/m^2 (male) or LVMI $\leq 95$ g/m^2 (female) and RWT>0.42

Eccentric hypertrophy, EH: LVMI>115g/ m^2 (male) or LVMI>95g/ m^2 (female) and RWT $\leq$ 0.42

Concentric hypertrophy, CH: LVMI>115g/  $m^2$  (male) or LVMI>95g/ m2 (female) and RWT>0.42

Reference Values for Chinese (EMINCA) and Configuration Analysis Based on Ganau Typing:

Normal left ventricular geometry, NG: LVMI $\leq 108$ g/ m^2 (male) and RWT $\leq 0.51$  or LVMI $\leq 99$ g/ m^2 (female) and RWT>0.49

Concentric remodeling, CR: LVMI≤108g/ m^2 (male) and RWT>0.51 or LVMI≤99g/ m^2 (female) and RWT>0.49

Eccentric hypertrophy, EH: LVMI>108g/ m^2 (male) and RWT≤0.51or LVMI>99g/ m^2 (female) and RWT≤0.49

Concentric hypertrophy, CH: LVMI>108g/ m^2 (male) and RWT>0.51 or LVMI>99g/

 $m^2$  (female) and RWT>0.49

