## (3) Group analysis:

1) For the healthy volunteers and hypertensive patients enrolled in the group: between 9:00

a.m. and 17:00 p.m. on the day of enrollment, at an interval of more than 4 hours, the patients performed two echocardiographic examinations in a calm state, measured and recorded their blood pressure at the same time (three measurements at an interval of 1-2 minutes), and measured the indicators at the two baseline levels on the day of enrollment. The changes of left ventricular global longitudial strain (GLS) and myocardial work (MW) in hypertension and healthy volunteer were compared, and the correlation between them and the changes of blood pressure was analyzed;

2) Analysis for hypertensive patients with different left ventricular configurations: configuration analysis was conducted based on the left ventricular remodeling standards recommended by ASE/EACVI 2015 guidelines and the EMINCA study combined with Ganau classification. Hypertensive patients were divided into normal left ventricular configuration group, left ventricular remodeling group, left ventricular eccentric hypertrophy group and left ventricular concentric hypertrophy group. Baseline, 12months, 24months, 36months and 48months echocardiography images were recorded and analyzed, compared the cardiac structure and functional indicators, and recorded clinical adverse events;

(2) Analysis for hypertensive patients with different left atrial configurations: according to the abnormal threshold of left atrial enlargement recommended by ASE/EACVI 2015 guidelines and the standard of Chinese left atrial enlargement recommended by EMNICA study, hypertensive patients were divided into normal left atrial group and left atrial enlargement group. Baseline, 12months, 24months, 36months and 48months echocardiography images were recorded and analyzed, compared the cardiac structure and functional indicators, and recorded clinical adverse events.

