#### (4) Analysis of main endpoint events:

1) Cox regression was used to analyze the predictive value of different types of left ventricular remodeling and left atrial enlargement on adverse cardiovascular events. ROC analysis was used to compare the incremental effect of left ventricular remodeling, left ventricular hypertrophy and left atrial enlargement on the predictive ability of hypertensive cardiovascular events; NRI [net corrected classification, i.e. (new sensitivity + new specificity) - (old sensitivity + old specificity)] was used to evaluate and compare the ability

of left ventricular remodeling, left ventricular hypertrophy and left atrial enlargement to re stratify and optimize the risk of cardiovascular events in hypertension. Multivariate regression analysis was used to analyze the factors affecting left ventricular remodeling and left atrial enlargement in hypertension.

2) The incidence time of adverse cardiovascular events was stratified by left ventricular remodeling, left ventricular hypertrophy and left atrial enlargement. Cox regression analysis was used to calculate the hazard ratio and its bilateral 95% confidence interval of different influencing factors.

(5) Statistical software: SAS 9.4 or SPSS software was used for analysis. Bilateral tests were used for statistical tests.  $P \le 0.05$  were considered statistically significant.

(6) Interim analysis: No interim analysis will be conducted in this study. If special cases occur, the main research center, researchers and statistical experts will discuss and decide.

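### The EMINCA rule for normal geometry in women repeats the rule for concentric remodeling, so no woman with LVMI≤99 g/m² falls in exactly one class

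*Protocol*

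**What the plan says.** Protocol, Groups, item (1), lists two sets of limits for the same four classes: normal geometry (NG), concentric remodeling (CR), eccentric hypertrophy (EH) and concentric hypertrophy (CH). The EMINCA set is sex-specific for both LVMI and RWT.

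- NG, men: "LVMI $\leq 108$ g/ m 2 (male) and RWT $\leq 0.51"; women: "LVMI $\leq 99$ g/ m 2 (female) and RWT>0.49".
- CR, men: "LVMI≤108g/ m 2 (male) and RWT>0.51"; women: LVMI at or below 99 and RWT above 0.49, the same two conditions as in the NG line.
- EH, women: "LVMI>99g/ m 2 (female) and RWT≤0.49".
- CH: "LVMI>108g/ m 2 (male) and RWT>0.51 or LVMI>99g", where the female part continues with RWT above 0.49.

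The classes are then used in two places under Statistical Treatment. Item (3), Group analysis, applies the ASE/EACVI limits and "the EMINCA study combined with Ganau classification" and states: "Hypertensive patients were divided into normal left ventricular configuration group, left ventricular remodeling group", followed by the two hypertrophy groups. Item (4), Analysis of main endpoint events, states: "Cox regression was used to analyze the predictive value of different types of left ventricular remodeling". No other part of the protocol restates or corrects the female EMINCA limit for NG.

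**The concern.** Four classes built from two dichotomies should split the patients with no gap and no overlap. Here two classes share one definition, and the low-LVMI, low-RWT combination in women, which is what normal geometry is meant to describe, has no class at all.

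This matters because comparing standards is the purpose of the study: the Objectives section refers to remodeling judged by different standards, and the Research Design section asks how the choice of standard bears on treatment and prognosis. NG is also the natural reference class for the other three. If the rules were programmed as printed, women with LVMI≤99 and RWT≤0.49 would drop out as unclassified. Those with RWT>0.49 would become NG or CR according to which rule the code happens to test first. The second fault is the harder one to notice, because sequential code gives such a woman a label without any warning.

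**Working it through.** The protocol states no figure to reproduce here, so the check is one of logic, using only its own cut-offs.

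**Inputs** (Protocol, Groups, item 1, EMINCA limits): LVMI 108 g/m² and RWT 0.51 for men; LVMI 99 g/m² and RWT 0.49 for women. Two sexes × two LVMI levels × two RWT levels give 2 × 2 × 2 = 8 cells. The four printed rules are applied to each cell.

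| Sex | LVMI | RWT | Classes met as printed | Classes met with female NG at RWT≤0.49 |
|---|---|---|---|---|
| Men | ≤108 | ≤0.51 | NG | NG |
| Men | ≤108 | >0.51 | CR | CR |
| Men | >108 | ≤0.51 | EH | EH |
| Men | >108 | >0.51 | CH | CH |
| Women | ≤99 | ≤0.49 | none | NG |
| Women | ≤99 | >0.49 | NG and CR | CR |
| Women | >99 | ≤0.49 | EH | EH |
| Women | >99 | >0.49 | CH | CH |

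As printed, 6 of 8 cells lead to exactly one class, 1 to none and 1 to two. The two faulty cells together contain every woman with LVMI≤99, so the share of these women with a unique class is 0%, whatever the distribution of RWT. With the sign changed, 8 of 8 cells lead to exactly one class. Coding the rules literally over a grid of LVMI 50 to 180 and RWT 0.20 to 0.80 gave the same pattern, before and after the change.

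**Worked cases, women:**

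- LVMI 80, RWT 0.40. ASE/EACVI (limits 95 and 0.42): NG. EMINCA as printed: no class. Corrected: NG.
- LVMI 80, RWT 0.45. ASE/EACVI: CR. EMINCA as printed: no class. Corrected: NG.
- LVMI 80, RWT 0.50. ASE/EACVI: CR. EMINCA as printed: NG and CR. Corrected: CR.

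The second case is a woman whom the two standards classify differently, which is what the study sets out to examine. As printed she has no EMINCA class to compare.

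**What is not touched:** all EMINCA classes in men; EH and CH in women; all ASE/EACVI classes; the left atrial groups, which use LAVI only; and the split into hypertrophy and no hypertrophy, which depends on LVMI alone and underlies the sample size.

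**The case against.** The strongest reply is that this is a one-character misprint that the section itself resolves. The female EH and CH lines divide at 0.49, the male NG and CR lines divide at 0.51 in the expected direction, and the ASE/EACVI lines follow the same pattern at 0.42. NG and CR are named as separate groups, so only one reading is coherent. The classes are calculated from stored measurements, so enrolment and data collection are unharmed, and a careful programmer would notice the empty cell. It is also possible that the sign is right in the sponsor's source file and was altered when the document was converted to text.

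Most of this stands. The intended sign can be inferred, no data are at risk, and a conversion fault cannot be fully excluded, although the sign stands in running text and the three other limits in the same line carry the expected ≤. But being easy to infer makes the repair easy; it does not make the text right. This is the protocol's only operational definition of the classes, two planned analyses rest on it, and the overlapping cell can be resolved arbitrarily without any warning.

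**Conclusion.** The point holds. As printed, the female EMINCA rules for NG and CR are identical, and every woman with LVMI≤99 g/m² meets either no class or two. For these women, neither the EMINCA four-group comparison nor the EMINCA Cox analysis by remodeling type can be carried out as written. The conclusion rests on the printed cut-offs alone and needs no outside figure.

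No number of patients is given: the protocol states neither the sex split nor the distribution of RWT, and it does not say which standard defines the hypertrophy quota per center. The effect on any hazard ratio cannot be sized for the same reason. The correction must be made before analysis because it concerns a class boundary for the main endpoint analysis, even though it is small.

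**What to change.** Change the female part of the EMINCA normal-geometry line to LVMI≤99 g/m² and RWT≤0.49, the complement implied by the female CR, EH and CH lines, after comparing the line with the sponsor's source file. Before analysis, test the classification program on one point from each of the eight cells, and confirm that every enrolled hypertensive patient with LVMI and RWT available falls in exactly one of the four classes under each standard.

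The cost is a one-sign protocol correction, submitted to the Ethics Committee as the protocol requires for any modification, and a short code check. No patient, visit or measurement is affected.

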## (2) Left atrium remodeling groups:

## 2015 ASE/EACVI guideline standard:

Left atrium enlargement groups: LAVI>34ml/m^2 (male, female)

## **Reference Values for Chinese (EMINCA) with BSA indexed:**

Left atrium enlargement groups: LAVI>34.3ml/m^2 (male) or LAVI>35.5ml/m^2

(female)

### Inclusion criteria for hypertension:

- (1) Age 30-75 years old;
- (2) No antihypertensive drugs were used and three blood pressure measurements were conducted on different days, with systolic blood pressure ≥ 140 mmHg (1 mmHg=0.133 kPa) and/or diastolic blood pressure ≥ 90 mmHg; or have a history of hypertension and are using antihypertensive drugs, even if the blood pressure is lower than 140/90 mmHg;
- (3) Left ventricular ejection fraction was normal (LVEF  $\geq 0.5$ ).
- (4) All patients agreed to participate in the experiment and signed the informed consent form.

#### Exclusion criteria for hypertension:

- Secondary hypertension caused by renal parenchymal diseases, renal vascular diseases, coarctation of aorta and endocrine system diseases;
- (2) Severe cardiovascular and cerebrovascular diseases; heart valve disease; persistent atrial fibrillation and severe arrhythmia; previously undergone cardiovascular disease surgery;
- (3) Abnormal liver function; abnormal renal function and diabetes;
- (4) Pregnant or breastfeeding women;
- (5) Expected survival time due to non-cardiovascular disease<4 years;
- (6) Patients with poor echocardiographic image quality.

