## **EFFICACY ASSESSMENT**

Primary study endpoints: emerging atrial fibrillation, transient ischemic attack (TIA) or stroke, unstable angina, myocardial infarction, heart failure, coronary revascularization, cardiovascular death; Secondary study endpoints: decreased cardiac function with preserved ejection fraction; new cardiac remodeling; aortic aneurysm or aortic dissection; ECG showed that QTc (QT interval corrected by heart rate) was more than 500ms or QTc was longer than the baseline level for more than 60ms, emerging torsade de pointes ventricular tachycardia and other serious arrhythmias; the relationship between the deviations of blood pressure within the same day and the difference of cardiac function indexes.

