#### (2) Accessory examination

- 1) ECG examination: use resting ECG to evaluate arrhythmia and ST-T changes, etc.
- 2) Laboratory tests:

Fasting for more than 6 hours, blood routine, urine routine, fasting blood glucose, alanine aminotransferase, aspartate aminotransferase, blood urea nitrogen, creatinine, plasma total cholesterol, triglyceride, low-density lipoprotein cholesterol, high-density lipid Protein cholesterol, high-sensitivity C-reactive protein, prothrombin time, serum troponin, NT-proBNP.

3) Transthoracic echocardiography:

Two-dimensional dynamic images of left ventricular parasternal long axis, apical fourchamber heart, apical two-chamber heart, apical long axis, left ventricular apex level, papillary muscle level, and mitral valve level short-axis view; measure left ventricular ejection fraction (LVEF); Pulse wave Doppler was used to obtain the diastolic mitral valve orifice blood flow spectrum, and tissue Doppler was used to obtain the mitral valve annulus motion spectrum, and E/e' was calculated; Using speckle tracking imaging (STI) ultrasound technology to measure global longitudinal strain (GLS)/strain rate, global circumferential strain, global radial strain, global area strain (3D-GAS), left ventricular torsion, left ventricular rotation/untwisting speed, systolic dissynchrony index (SDI) and right ventricular free wall systolic peak strain (RVFWS) and so on.

4) Carotid ultrasound examination: the patient was the occipital supine position, with slightly raised jaw, the face was turned to one side, and the sternocleidomastoid muscle was fully exposed. The probe scans from the posterior edge of the sternocleidomastoid muscle to display the long axis and short axis images of the common carotid artery, internal and external carotid arteries, and bifurcation. The intima-media thickness, internal diameter and blood flow velocity were measured at 1-2 cm before the

bifurcation of the common carotid artery.

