## (3) The main observation and detection indicators of the first follow-up

Hypertensions will be followed up in the 12th, 24th, 36th and 48th months after being enrolled in this study. They can be followed up through outpatient service or telephone. Each follow-up shall not exceed two weeks before and after the specified follow-up time. Perform physical examination, ECG examination, laboratory examination, echocardiography, etc. Record the treatment and whether there are adverse cardiovascular clinical events (myocardial infarction, heart failure, cardiovascular death, unstable angina requiring hospitalization, aortic aneurysm or aortic dissection, stroke). Record the time when the adverse event occurred.

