## **DIAGRAM OF RESEARCH SCHEME**

## **CHART OF RESEARCH SCHEME**

Follow-up time	0 month	12th month	24th month	36th month	48th month
Information	•				
Medical history	•				
Inclusion Criteria	•				
Informed consent	•				
Electrocardiogram	•	•	•	•	•
Physical examination	•	•	•	•	•
Laboratory examination	•				
Echocardiography	•		•		•
Arterial ultrasound	•		•		•
Drugs treatments	•	•	•	•	•
Adverse events		•	•	•	•

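### Emerging atrial fibrillation is a primary event with no link to AF history or the baseline ECG, although patients with non-persistent AF can enrol; the 500 ms QTc criterion also lacks a baseline condition

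*Protocol*

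**What the plan says.** - **Entry.** Item (2) of the protocol's exclusion criteria for hypertension removes "persistent atrial fibrillation and severe arrhythmia". It does not name paroxysmal AF or a history of AF, and it does not define severe.
- **Primary endpoint.** The Efficacy Assessment section opens the list of primary events with "emerging atrial fibrillation, transient ischemic attack (TIA) or stroke". It does not define emerging, sets no look-back period and does not say who is at risk for this component.
- **Baseline information.** The chart of the research scheme schedules medical history and an ECG at month 0. The accessory examination section says to "use resting ECG to evaluate arrhythmia and ST-T changes". Neither source is linked to the AF component.
- **Follow-up.** The chart repeats the ECG at months 12, 24, 36 and 48. The event-recording instruction reads "Record the treatment and whether there are adverse cardiovascular clinical events (myocardial infarction, heart failure, cardiovascular death, unstable angina requiring hospitalization" and goes on to aortic disease and stroke. AF is not in that list.
- **Analysis.** The full analysis set holds all enrolled hypertensive patients. The main analysis states that "Cox regression was used to analyze the predictive value of different types of left ventricular remodeling and left atrial enlargement on adverse cardiovascular events", and it adds ROC and NRI comparisons for the same exposures.
- **QTc.** A secondary endpoint is met when "QTc (QT interval corrected by heart rate) was more than 500ms or QTc was longer than the baseline level for more than 60ms".

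**The concern.** An incident endpoint needs a population free of the condition at time zero, or a rule that separates recurrence from onset. Here the eligibility criteria let some patients with earlier AF in, and the endpoint contains no such rule. Twenty centres could read emerging in two ways: new to the patient, or new on a study tracing.

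The analysis most exposed is that of left atrial enlargement. If earlier AF is commoner in patients with large atria, a recurrence scored as onset would make atrial size appear to predict something that preceded enrolment. If it is spread evenly over the groups compared, it would dilute the contrasts instead.

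The QTc criterion has the same structural weakness in a plainer form. One arm measures change from baseline and the other does not, so a stable baseline abnormality can be recorded as an outcome.

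**Working it through.** **1. Can a patient with earlier AF reach the AF component?** Take a patient with known paroxysmal AF who is in sinus rhythm at month 0.
- Exclusion item (2): the AF is not persistent. Whether it is a severe arrhythmia is left to the site, so the patient may be eligible.
- Full analysis set: included. The per-protocol set does not remove the patient either, because no exclusion has been breached.
- Follow-up ECG showing AF: the endpoint text gives no condition under which this is not an event.
- Left atrial Cox, ROC and NRI analyses: no restriction by AF history.

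**2. QTc, read literally.** The exclusion criteria contain no QTc limit. A patient at 505 ms at month 0 and 505 ms at month 12 has a change of 0 ms. The change arm (more than 60 ms) is not met. The absolute arm (more than 500 ms) is met.

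**3. How sensitive is the study to misscored events?** The protocol gives no prevalence of earlier AF and no event rates by atrial size, so nothing can be computed for the left atrial exposure. The only planned rates are for hypertrophy against no hypertrophy, in the sample size section: p1 = 4.9%, p2 = 2.2%, two-sided alpha 0.05, 986 per group. Power is not stated.

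Reproducing the plan's figure, with p̄ = 0.0355:

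n = [1.960·√(2·0.0355·0.9645) + 1.282·√(0.049·0.951 + 0.022·0.978)]² / 0.027² = 985 at 90% power. This agrees with the stated 986. At 80% power the same formula gives 737.

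Expected events at 986 per group are 986 × 0.049 = 48 and 986 × 0.022 = 22.

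Now assume that a fraction q of otherwise event-free patients is scored with AF that preceded entry, so that p′ = p + q(1 − p). All values of q are assumptions.

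| q in both groups | Rates | Extra events per group | Rate ratio | Power |
|---|---|---|---|---|
| 0 | 4.9% / 2.2% | 0 | 2.23 | 90% |
| 0.5% | 5.4% / 2.7% | about 5 | 2.00 | 86% |
| 1% | 5.9% / 3.2% | 9 to 10 | 1.84 | 82% |
| 2% | 6.8% / 4.2% | about 19 | 1.64 | 73% |

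With unequal q and no true difference (2.2% in both groups):

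| q, group 1 / group 2 | Spurious rate ratio | Chance of a significant result |
|---|---|---|
| 1% / 0.5% | 1.18 | 10% |
| 2% / 1% | 1.31 | 21% |
| 3% / 1% | 1.62 | 59% |

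The tables show two things. With so few expected events, a small fraction matters. And the direction depends entirely on how earlier AF is distributed, which the protocol does not tell us.

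**The case against.** The strongest reply is that emerging already means new. Medical history and ECG are taken at month 0, so known AF can be recognised, and the publication section mentions a clinical event determination committee that could apply the distinction. This largely stands: the protocol contains no instruction to count old AF. It does not remove the gap, because the month 0 information is not tied to the endpoint and the protocol gives that committee no AF criterion.

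A second reply is that the same exclusion item also removes severe arrhythmia and severe cardiovascular disease, which may catch some non-persistent AF. That is fair, so it would be wrong to say that persistent AF is the only form excluded. With both terms undefined, however, and one AF type named expressly, a site could reasonably admit the others.

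A third is that capture may be low rather than high. Rhythm is checked by a resting ECG once a year, follow-up by telephone is allowed, and the follow-up event list omits AF. This stands, and it is a reason not to put a number on the misscored events.

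A reader might infer that the left atrial hazard ratio, ROC and NRI are necessarily pushed upward. The protocol does not support that. It gives no AF history by atrial size, and equal misscoring in the hypertrophy comparison moves the rate ratio toward 1.

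On QTc, the example patient is hypothetical and the endpoint is secondary. Both are true, but the wording admits the case as it stands.

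**Conclusion.** The point holds as a missing at-risk rule, not as a demonstrated bias. Patients with paroxysmal or past AF can enrol, a recurrence can be scored as a primary event, and these patients remain in the left atrial analyses, where reverse causation is plausible. Its size and direction there cannot be derived from the protocol. The hypertrophy figures are illustrations that rest on assumed fractions of 0.5% to 3%, on the protocol's 4.9% and 2.2%, and on an inferred 90% power. The protocol does not say whether those planned rates include AF.

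The QTc point follows from the wording alone: a patient already above 500 ms at entry meets the secondary endpoint with no change.

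The mismatch between the primary endpoint, which includes AF, and the follow-up event list, which does not, is a further inconsistency. Its effect would be under-recording.

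**What to change.** 1. In Efficacy Assessment, count emerging AF only as the first documented AF in a patient with no AF of any type in the month 0 history or on the baseline ECG. Record AF history as an explicit month 0 item. Patients with prior AF stay in the study for the other components.
2. Repeat the left atrial enlargement Cox, ROC and NRI analyses without patients with prior AF, as a sensitivity analysis.
3. Count the 500 ms QTc arm only when baseline QTc was 500 ms or less.
4. Reconcile the follow-up event list with the primary endpoint so that AF is recorded.

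**Cost.** Eligibility does not change, and the history and ECG are already scheduled at month 0, so this needs endpoint wording, one baseline flag and one extra set of analyses. Patients with prior AF can no longer score the AF component, so the event count may be slightly smaller and the composite differs slightly for them. The rule acts only on documented AF; silent AF that a resting ECG misses would still be counted when first seen.
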